### 5.3 Laboratory parameters derivations

Grade categorization of lab values will be assigned programmatically as per NCI Common Terminology Criteria for Adverse Events (CTCAE) version 5.0. The calculation of CTCAE grades will be based on the observed laboratory values only, clinical assessments will not be taken into account. The criteria to assign CTCAE grades are given in Novartis internal criteria for CTCAE grading of laboratory parameters (embedded below). The latest available version of the document based on the underlying CTCAE version v5.0 at the time of analysis will be used. For laboratory tests where grades are not defined by CTCAE v5.0, results will be graded by the low/normal/high (or other project-specific ranges, if more suitable) classifications based on laboratory normal ranges.

A severity grade of 0 will be assigned for all non-missing lab values not graded as 1 or higher. Grade 5 will not be used. For laboratory tests that are graded for both low and

high values, summaries will be done separately and labelled by direction, e.g., sodium will be summarized as hyponatremia and hypernatremia.

EASE LAB - CTC  
grades in Novartis On

### Imputation Rules

CTCAE grading for blood differentials is based on absolute values. However, this data may not be reported as absolute counts but rather as percentage of white blood cells (WBC).

If laboratory values are provided as ' $<X$ ' (i.e. below limit of detection) or ' $>X$ ', prior to conversion of laboratory values to SI unit, these numeric values are set to  $X$ .

The following rules will be applied to derive the WBC differential counts when only percentages are available for a xxx differential

$\text{xxx count} = (\text{WBC count}) * (\text{xxx \%value} / 100)$

The following rules will be applied to derive the WBC differential percentages when only differential counts are available for a xxx differential

$\text{xxx \%value} = (\text{xxx count} \times 100) / \text{WBC count}$

Further derivation of laboratory parameters might be required for CTCAE grading. For instance, corrected calcium can be derived using the reported total calcium value and albumin at the same assessment using the following formula:

Corrected Calcium (mg/dL) = Calcium (mg/dL) – 0.8 [Albumin (g/dL)-4]

In order to apply the above formula, albumin values in g/L will be converted to g/dL by multiplying by 0.1 and calcium values in mmol/L will be converted to mg/dL by dividing by 0.2495. For calculation of laboratory CTCAE grades 0 and 1, the normal range for derived corrected calcium is set to the same limits (in mg/dL) as for calcium.

CTCAE grades for the derived absolute WBC differential counts (neutrophils, lymphocytes) and corrected calcium will be assigned as described above for grading.

### 5.3.1 Derivation of PCR results and loss of response(s)

Scaling towards an international standard will be performed for all molecular results using laboratory specific conversion factors. In this process, the raw ratio between BCR-ABL and the control gene ABL is calculated and multiplied by the lab -specific conversion factor ([\[Branford and Hughes 2006\]](#)). Therefore, using the international unit, the BCR-ABL ratio will be presented in %. The MRDx assay using PAXgene™ Blood RNA tubes from MMD laboratory will be used in this study. The lab conversion factor for this assay is 1.1.

The BCR-ABL ratio in IS % is calculated by multiplying the raw BCR-ABL ratio with the lab-specific conversion factor and then by 100:

$$\text{BCR-ABL ratio (in \%)} = (\text{BCR-ABL} / \text{ABL}) * \text{conversion factor} * 100$$

For consistency with elsewhere reported molecular response rates, the result may be expressed also as log-reduction. This is defined as the following:

$$\text{BCR-ABL Log-Reduction} = -\log_{10}(\text{BCR-ABL ratio in \%})$$

For example,  $-\log_{10}(0.001) = 3$  log reduction for a ratio of 0.1%.

The following binary variables will be used when molecular response is reported.

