**Table 5-3 Response categories for molecular response**

MR (Molecular Response)		BCR-ABL ratio (%)	Log-reduction category
MMR	Yes	$\leq 0.1\%$	$\geq 3$ -log reduction
	No	$> 0.1\%$	< 3-log reduction
MR2	Yes	$\leq 1\%$	$\geq 2$ log reduction
	No	$> 1\%$	< 2 log reduction
MR4	Yes	$\leq 0.01\%$	$\geq 4$ log reduction
	No	$> 0.01\%$	< 4 log reduction
MR4.5	Yes	$\leq 0.0032\%$	$\geq 4.5$ -log reduction
	No	$> 0.0032\%$	< 4.5-log reduction

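### The SAP 5.3.1 log-reduction formula is 2 logs too low as printed; it needs a one-line correction, but response rates under SAP 2.8.2 would not change

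*SAP*

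**What the plan says.** SAP 5.3.1 (Derivation of PCR results and loss of response(s)) sets out three steps.

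- The ratio in % on the international scale (IS) is obtained by "multiplying the raw BCR-ABL ratio with the lab-specific conversion factor and then by 100". For the conversion factor it says: "The lab conversion factor for this assay is 1.1".
- It adds that "the result may be expressed also as log-reduction", and gives the formula as minus log10 of the BCR-ABL ratio in %.
- It then works an example: minus log10 of 0.001 is a 3 "log reduction for a ratio of 0.1"%.

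Table 5-3 ("Response categories for molecular response") follows. For each level it lists a percentage cut-off beside a log-reduction cut-off: 1% with 2 logs (MR2), 0.1% with 3 (MMR), 0.01% with 4 (MR4) and 0.0032% with 4.5 (MR4.5). SAP 2.8.2 and Protocol 8.4.1 use the same four pairs.

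**The concern.** The formula and the example directly beneath it do not agree. The SAP's own definition stores a ratio of 0.1% as the number 0.1, because the multiplication by 100 has already been done. The example puts in 0.001, which is the proportion. A programmer who follows the formula and one who follows the example would produce different values for every sample.

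At stake is the scale of any log-reduction value in a table, listing or figure, and the consistency of the two columns of Table 5-3, which defines the binary response variables. The SAP does not say which column decides a response.

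**Working it through.** **Inputs** (SAP 5.3.1 and Table 5-3): ratio in % = raw ratio × 1.1 × 100; printed formula LR = −log10(ratio in %); worked example 3 for 0.1%; cut-off pairs as in Table 5-3.

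**The SAP's own figure.** With the printed formula and the defined percentage, −log10(0.1) = 1, so the stated 3 is not reproduced. With the proportion, −log10(0.1/100) = −log10(0.001) = 3, so it is. The example is arithmetically right but does not follow from the formula above it.

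**All four cut-offs.**

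| Level | Ratio in % | Printed: −log10(%) | Proportion: −log10(%/100) | Table 5-3 |
|---|---|---|---|---|
| MR2 | 1 | 0 | 2 | 2 |
| MMR | 0.1 | 1 | 3 | 3 |
| MR4 | 0.01 | 2 | 4 | 4 |
| MR4.5 | 0.0032 | 2.495 | 4.495 | 4.5 |

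The gap between the two calculations is log10(100) = 2 at every ratio, whatever the conversion factor.

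**Above 1%.** A raw ratio of 0.05 gives 0.05 × 1.1 × 100 = 5.5%. The printed formula returns −log10(5.5) = −0.74; the proportion gives 2 − 0.74 = 1.26. At 10%, the boundary of the resistance subgroup in SAP 2.2.1, the values are −1 and +1.

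**If the log column alone decided response, with the printed formula.** The percentage needed to reach k logs would be 10^(−k):

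- MR2: 0.01% or less, instead of 1%
- MMR: 0.001% or less, instead of 0.1%
- MR4: 0.0001% or less, instead of 0.01%
- MR4.5: about 0.00003% or less, instead of 0.0032%

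For MMR, every patient above 0.001% and up to 0.1% would be lost as a responder.

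**Under SAP 2.8.2.** Each response there is met by the log criterion *or* the IS percentage. The mis-scaled log criterion is stricter: 0.001% or less lies inside 0.1% or less, and the other levels behave alike. The union is therefore just the percentage criterion, and no responder is gained or lost.

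**MR4.5 boundary after correction.** 10^(−4.5) as a percentage is 0.00316%. A ratio above 0.00316% and up to 0.0032% meets the percentage cut-off but has a log reduction slightly below 4.5. This is rounding of the cut-off, separate from the factor of 100.

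**The case against.** The strongest reply is that the intended calculation is not in doubt. The example prints both the substitution and the result, and Table 5-3 agrees with it. Since 0.1% is mathematically 0.001, the example can be read as showing how the formula is meant to be applied. The log form is optional, and the visible secondary analyses are proportions and Kaplan-Meier estimates, with no table of log-reduction values specified. The loss definitions for MR2 and MMR (SAP 5.3.1), treatment failure (Protocol 9.1.1) and the resistance subgroup (SAP 2.2.1) all work on the IS percentage. A literal error would also be conspicuous, because ratios above 1% would show negative reductions.

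Most of this stands, and it limits the effect. It does not rescue the formula. The SAP fixes the unit with an explicit multiplication by 100, in words and in symbols, so the quantity inside the logarithm is 0.1. This is also the only formula the SAP gives for the variable, and Protocol 8.4.1 provides for either the log reduction or the percent ratio to be calculated for each sample.

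A reader might infer that molecular response rates will be reported wrongly, or that a patient at 0.1% will be reported with a 1-log reduction. The documents do not support either. SAP 2.8.2 keeps the rates on the percentage criterion, and the SAP's own example assigns 3 logs at 0.1%.

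**Conclusion.** The printed formula is wrong by exactly 2 logs (100-fold) at every ratio and conflicts with the example and all rows of Table 5-3. That follows from the SAP's text and needs no outside assumption.

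The consequences are conditional. Log-reduction values would be wrong if they are reported and if the formula is programmed as printed. Responders would be undercounted only if, in addition, flags came from the log column alone; the documents give no distribution of ratios from which to size that. Under the definitions in SAP 2.8.2, response rates and times to response are unaffected. Molecular response is a secondary, descriptive endpoint here, and the primary endpoint is safety. This is a minor correction of a wrong derivation formula, not an error that puts a planned result in doubt.

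**What to change.** In SAP 5.3.1, change the formula to −log10(BCR-ABL ratio in % / 100), equivalently 2 − log10(BCR-ABL ratio in %). This reproduces the worked example and Table 5-3 (4.495 for 4.5 in the last row).

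Add one sentence at Table 5-3 stating that response flags are taken from the IS percentage cut-offs and that the log column is descriptive. This also settles the MR4.5 boundary.

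Confirm that the programmed derivation uses the proportion. The cost is one line and one sentence of SAP text plus a check of existing code; no data collection or endpoint definition changes.

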**Table 5-3 Response categories for molecular response**

MR (Molecular Response)		BCR-ABL ratio (%)	Log-reduction category
MMR	Yes	$\leq 0.1\%$	$\geq 3$ -log reduction
	No	$> 0.1\%$	< 3-log reduction
MR2	Yes	$\leq 1\%$	$\geq 2$ log reduction
	No	$> 1\%$	< 2 log reduction
MR4	Yes	$\leq 0.01\%$	$\geq 4$ log reduction
	No	$> 0.01\%$	< 4 log reduction
MR4.5	Yes	$\leq 0.0032\%$	$\geq 4.5$ -log reduction
	No	$> 0.0032\%$	< 4.5-log reduction

## Loss of Responses

Loss of MR2 is defined as increase of BCR-ABL/ABL to  $> 1\%$  by international scale (IS). BCR-ABL less than 1% according to the IS can be regarded as an equivalent to CCyR. Loss of MR2 must be confirmed by subsequent sample analysis within 4 to 6 weeks.

Loss of MMR is defined as increase of BCR-ABL/ABL to  $> 0.1\%$  by international scale (IS) in association with a  $\geq 5$ -fold rise in BCR-ABL from the lowest value achieved on study treatment and replicated by a second analysis of the same sample. Loss of MMR must be confirmed by subsequent sample analysis within 4 to 6 weeks showing loss of MMR associated with a  $\geq 5$ -fold rise in BCR-ABL from the lowest value achieved on study treatment, unless it is associated with confirmed loss of CHR to AP/BC or CML-related death.

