The Assessment Schedule ([Table 8-1](#)) lists all of the assessments when they are performed. All data obtained from these assessments must be supported in the participant's source documentation.

Participants should be seen for all visits/assessments as outlined in the assessment schedule ([Table 8-1](#)) or as close to the designated day/time as possible. Missed or rescheduled visits should not lead to automatic discontinuation. Participants who prematurely discontinue the study for any reason should be scheduled for a visit as soon as possible, at which time all of the assessments listed for the final visit will be performed. At this final visit, all dispensed investigational product should be reconciled, and the adverse event and concomitant medications recorded on the CRF.

[figure not shown]
No eCRF will be used as a source document.

(S) is defined as "Source"

[figure not shown]
(D) is defined as "Data Based"

Table 8-1 Assessment schedule

[figure not shown]
| Visit name | Category | Protocol Section 8 | Screening Phase | Treatment Phase | | | | | | | | | | | | | | | |
|------------------------------------|----------|--------------------|----------------------------------|-----------------|--------------|--------|--------|---------|---------|---------|---------|---------|---------|---------|---------|---------|---------|---------|--|
| | | | | Week 1 Day 1 | Week 2 Day 1 | Week 4 | Week 8 | Week 12 | Week 16 | Week 20 | Week 24 | Week 28 | Week 32 | Week 36 | Week 40 | Week 44 | Week 48 | Week 52 | |
| Obtain Informed Consent | D | | X (Screening window -56 days) | | | | | | | | | | | | | | | | |
| Eligibility checklist/registration | D | | X | | | | | | | | | | | | | | | | |
| Cohort Assignment | D | 6.3.2 | X | | | | | | | | | | | | | | | | |
| Demography | D | 8.2 | X | | | | | | | | | | | | | | | | |
| Inclusion/exclusion criteria | D | 5.1 | X | | | | | | | | | | | | | | | | |
| Medical History | D | 8.2 | X | | | | | | | | | | | | | | | | |
| Disease History | D | 8.2 | X | | | | | | | | | | | | | | | | |
| Mutation status | D | 8.2 | X | | | | | | | | | | | | | | | | |
| Prior antineoplastic therapy | D | 8.2 | X | | | | | | | | | | | | | | | | |
| Prior TKI therapy | D | 8.2 | X | | | | | | | | | | | | | | | | |

[figure not shown]
[figure not shown]
| Visit name | Category | Protocol Section 8 | Screening Phase Screening/ Baseline (Day -21 to -1) | Treatment Phase | | | | | | | | | | | | | | | |

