MR4.5 and related variables are defined as the following:

- Rate of MR4.5 where MR4.5 is defined as a ≥ 4.5 log reduction in BCR-ABL1 transcripts compared to the standardized baseline equivalent to $\leq 0.0032\%$ BCR-ABL1/ABL % by international scale as measured by RQ-PCR, confirmed by duplicate analysis of the same sample
- Time to MR4.5 defined as the time from the date of start of study treatment to the date of the first documented MR4.5
- Duration of MR4.5 defined as the time from the date of first documented MMR to the earliest date of loss of MR4.5, progression to AP or BC, or CML-related death

Loss of Responses

Loss of MR2 is defined as increase of BCR-ABL1/ABL to $> 1\%$ by international scale (IS). BCR-ABL less than 1% according to the IS can be regarded as an equivalent to CCyR. Loss of MR2 must be confirmed by subsequent sample analysis within 4 to 6 weeks.

Loss of MMR is defined as increase of BCR-ABL1/ABL to $> 0.1\%$ by international scale (IS) in association with a ≥ 5 -fold rise in BCR-ABL1 from the lowest value achieved on study treatment and replicated by a second analysis of the same sample. Loss of MMR must be confirmed by subsequent sample analysis within 4 to 6 weeks showing loss of MMR associated with a ≥ 5 -fold rise in BCR-ABL1 from the lowest value achieved on study treatment, unless it is associated with confirmed loss of CHR to AP/BC or CML-related death.

Mutational Analysis (T315I mutation)

Mutational analysis will be performed at a Novartis designated laboratory by Sanger sequencing for T315I mutation at Screening if T315I mutational analysis is not confirmed and upon confirmed loss of MMR and/or at end of treatment. Please see [Section 8.5.3](#).

The blood samples will be taken as described in [Table 8-1](#), and [Table 8-6](#).

Table 8-3 Blood samples (efficacy secondary endpoint)

| Sample Type | Volume | Visit | Time point |
|---|--|--|------------|
| Blood for BCR-ABL1 quantification by RQ-PCR | 20 mL | Screening/Baseline | Pre-dose |
| | 20 mL | Week 4 | Pre-dose |
| | 20 mL | Week 12 | Pre-dose |
| | 20 mL | Week 24 | Pre-dose |
| | 20 mL | Week 36 | Pre-dose |
| | 20 mL | Week 48 | Pre-dose |
| | 20 mL | Week 60 ^β | Pre-dose |
| | 20 mL | (Week 72) End of Treatment | Anytime |
| Blood for BCR-ABL1 Mutation analysis by Sanger Sequencing | 5 mL | Screening | Pre-dose |

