| | No sample collected - testing is performed on the "Blood for BCR-ABL1 quantification by RQ-PCR" sample | Upon confirmed loss of MMR and/or End of Treatment | Anytime |

β = only applicable if the visit is in-person

During the study, peripheral blood samples will be collected into PAXgene™ Blood RNA tubes for all RQ-PCR assessments. Detailed instructions for the collection, handling, and shipment of RQ-PCR and mutation samples are outlined in the [\[CABL001AUS04 Laboratory Manual\]](#).

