**Table 2-1 Time windows for molecular response (BCR-ABL1 quantification by RQ-PCR)**

Assessment	Target day of assessment	Time Interval
Baseline	≤ 1	≤ Day 1#
Week 4	29	Day 2 to day 57
Week 12	85	Day 58 to day 127
Week 24	169	Day 128 to day 211
Week 36	253	Day 212 to day 295
Week 48	337	Day 296 to day 421
Week 72	505	Day 422 to day 589

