### **Duration of CHR, MR2, MMR, MR4 and MR4.5**

Duration of Response (DOR) is the time from the date of the first documented molecular (MR2, MMR, MR4, MR4.5) or Hematologic (CHR) response to the date of first documented loss of that response or death due to any cause or progression to AP/BC, whichever occurs first.

The start date is the date of first documented response and the end date is defined as the date of the first documented loss of that response or death due to any cause or progression to AP/BC. Participants continuing without that event will be censored at the date of their last adequate molecular or hematologic response assessment.

DOR for each response level will be analyzed using the Kaplan-Meier Product-Limit method.

Estimates of DOR at specific timepoint and the 25th, median and 75th percentile of the DOR and their 95% confidence intervals will be provided, if applicable.

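### Loss of MR2 or MMR must be confirmed within 4 to 6 weeks, an interval that scheduled PCR draws from Week 12 on cannot meet, so duration of response can be overstated

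*SAP*

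**What the plan says.** **Definition.** In SAP 5.3.1 (Loss of Responses), loss of MR2 is a rise above 1% on the international scale, and "Loss of MR2 must be confirmed by subsequent sample analysis within 4 to 6 weeks". Loss of MMR is a rise above 0.1% with at least a five-fold increase over the lowest on-study value. Protocol 8.4.1 has the same definitions: "Loss of MMR must be confirmed by subsequent sample analysis within 4 to 6 weeks showing loss of MMR". For MMR only, the later sample is waived: "unless it is associated with confirmed loss of CHR to AP/BC or CML-related death".

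**Schedule.** Protocol Section 8 says that Table 8-1 "lists all of the assessments when they are performed". Table 8-3 gives one row per RQ-PCR draw, in the form "20 mL | Week 12 | Pre-dose", for screening, Weeks 4, 12, 24, 36, 48 and 60, and Week 72 or end of treatment. The Week 60 draw is "only applicable if the visit is in-person".

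**Analysis.** For duration of response, SAP 2.8.2 states that "the end date is defined as the date of the first documented loss of that response", or death from any cause, or progression to AP/BC. Patients without an event are censored at the last adequate assessment. SAP 2.8.3 censors duration of MMR at the last on-treatment PCR. Neither section says how to treat a first value over the threshold that has no second sample, or a second sample outside the interval.

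**Stopping rules.** Protocol 9.1.1 makes loss of MR2 a treatment failure requiring discontinuation and mentions no confirmation. For MMR it asks for two tests in a row, with no 4 to 6 week limit.

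**The concern.** The definition needs a second sample in a narrow interval, and the schedule does not supply one. Applied literally, a loss seen at Week 24 and seen again at Week 36 is not a confirmed loss.

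MR2 is the sharpest case. Loss of MR2 ends treatment, and a patient who leaves the study early has the final visit soon afterwards. That visit's PCR may come before day 28 or after day 42 from the first sample, and Table 8-3 has no draw after end of treatment. The patient was removed because response was lost, yet may enter the duration analysis as censored. Censoring that the event itself brings about is informative, and it pushes the Kaplan-Meier curve upward.

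At stake are the secondary endpoints duration of MR2 and duration of MMR, plus a choice about unconfirmed losses that would otherwise be made after the data are seen.

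**Working it through.** **Inputs.** Confirmation interval: 4 to 6 weeks, taken as 28 to 42 days after the first sample. PCR weeks: Protocol Table 8-3. Visit window: ±7 days from Week 4 (Protocol 8.1.4). Target days and analysis windows: SAP Table 2-1.

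**1. The plan's own target days.** Target day = 7 × week + 1. Weeks 4, 12, 24, 36, 48 and 72 give 29, 85, 169, 253, 337 and 505, exactly as in SAP Table 2-1.

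**2. Gaps between scheduled draws.** Smallest gap = nominal gap − 7 − 7 days.

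| Pair of draws | Nominal gap | Smallest gap |
|---|---|---|
| Weeks 4 and 12 | 56 days | 42 days (6 weeks) |
| 12–24, 24–36, 36–48; 48–60 and 60–72 if Week 60 is in person | 84 days | 70 days (10 weeks) |
| 48–72 if Week 60 is remote | 168 days | 154 days (22 weeks) |

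Only Weeks 4 and 12 can meet the 42-day limit, and only with the first visit a full week late and the second a full week early.

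**3. Where a redraw would fall.** Four weeks after Weeks 12, 24, 36 and 48 are Weeks 16, 28, 40 and 52. Protocol 8.1.4 lets all four be remote visits.

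**4. What the SAP windows would do to a redraw.** A redraw 28 to 42 days after an on-target Week 24 sample falls on days 169 + 28 = 197 to 169 + 42 = 211. The Week 24 window is days 128 to 211, and the SAP keeps the assessment closest to target, so the redraw would drop out of windowed values. SAP Table 2-1 also has no Week 60 slot. An on-target Week 60 draw is day 7 × 60 + 1 = 421, the last day of the Week 48 window (296 to 421); the Week 72 window is "Day 422 to day 589". A loss derived from windowed values could therefore miss samples that were actually taken.

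**5. Illustration of size.** The documents give neither the loss rate nor the share of losses redrawn in time, so both are assumed. Let p be the true loss by 48 weeks after first response and c the share confirmed in the interval. Deaths and AP/BC are ignored. If unconfirmed losses stay event-free to the last draw, apparent 48-week retention is 1 − c × p. For p = 20% and c = 50%: 1 − 0.5 × 0.2 = 0.90, against a true 0.80. A simulation of 40,000 responders, with exponential loss detected at the scheduled draws and unconfirmed losses censored either at the last draw or at the draw where they were found, gives:

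| Assumed loss by 48 weeks | All confirmed | Half confirmed | None confirmed |
|---|---|---|---|
| 10% | 90% | 95% | 100% |
| 20% | 80% | 90% | 100% |
| 30% | 70% | 84–85% | 100% |

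**6. MR4 and MR4.5.** Their durations are endpoints (SAP 1.2 and 2.8.2), but the loss definitions in Protocol 8.4.1 and SAP 5.3.1 cover only MR2 and MMR. SAP Table 5-3 gives yes/no cut-offs for attaining MR4 and MR4.5, not a rule for losing them.

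**The case against.** The strongest reply is that the redraw is already required: a rule that a loss must be confirmed in a set interval tells the site to take a sample. Visits are every 4 weeks, and the SAP lists unscheduled assessments. Parts of Table 8-1 and Section 8.5 are not visible, and collection details sit in a laboratory manual outside these documents. Patients who stop treatment are asked to return for scheduled assessments where possible, so a later PCR is not excluded. The endpoints are descriptive and secondary in a study whose primary objective is safety.

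Much of this stands. It makes the bias conditional and rules out some stronger readings.

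- A reader might infer that no loss can ever be confirmed. That is true only of scheduled pairs from Week 12 on.
- A reader might infer that a loss first seen at the last sample can never count. The MMR waiver, and death and AP/BC as duration events in their own right, contradict that.
- A reader might infer that each missed loss adds at least 12 weeks. The first gap is 8 weeks, and a loss censored at the draw where it was seen adds none.

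The reply does not remove the mismatch. Where the protocol wants extra tests it writes them down: unscheduled ECGs in Table 8-2, as-needed hematology and chemistry in Table 8-6, and mutation analysis on confirmed loss of MMR in Table 8-3. The visible RQ-PCR rows have no such trigger. Nor does the reply supply the missing rule for late or absent confirmation.

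**Conclusion.** The point holds in conditional form. The confirmation rule and the PCR schedule do not fit: from Week 12 on, the closest two scheduled draws can be is 70 days, against a limit of 42. Unless sites take an unscheduled redraw on time, real losses can fail the definition. If they are then censored under SAP 2.8.2 and 2.8.3, duration of MR2 and MMR is biased upward. The size cannot be derived from the documents; the table above shows only what assumed rates would do.

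It would go too far to say that duration is overstated as a fact, because neither document states that an unconfirmed loss is censored. It would also go too far to say that durations of MR4 and MR4.5 are biased short by single noisy values. Their loss is undefined, not defined by one value.

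This should be changed, since a cheap rule settles it. It does not affect the primary safety analysis.

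**What to change.** 1. **SAP 5.3.1, duration analysis.** Count a loss of MR2 or MMR as confirmed by the next available PCR at least 4 weeks later, with no upper limit, and date it at the first sample. Derive loss from all samples, including unscheduled ones, not from windowed values. Add two sensitivity analyses: one counting every first loss with no qualifying later sample (including one at end of treatment) as an event, and one keeping the strict 4 to 6 week rule. Record this in SAP Section 4 as a change from Protocol 8.4.1; that section now reports no change.
2. **MR4 and MR4.5.** Define their loss, with the same confirmation rule.
3. **Protocol.** Add a footnote to Tables 8-1 and 8-3 for the confirmatory RQ-PCR that the definition already requires. Reconcile the loss wording in 8.4.1 with that in 9.1.1 for both MR2 and MMR; which wording should govern stopping of treatment is for the sponsor to settle.

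**Cost.** A few sentences in the SAP, a footnote in two tables, a little extra analysis and an occasional blood draw. The SAP changes need no new data; the footnote helps only patients still being sampled. The downside is that some losses will be confirmed on later samples than the protocol definition foresees, which the strict-rule sensitivity analysis makes visible.
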